5.6.5. Clinical laboratory evaluation

Serum creatinine collected during the follow-up period will be tabulated as quantitative parameter by visit in raw data and change from baseline. If during the follow-up visits, the date of last renal function assessment is replicated then only the first measurement will be taken into account.

Serum creatinine will be presented in $\mu\text{mol/L}$. Therefore, conversion will apply for measurement in mg/L and mg/dL using the following conversion factors [1]:

From mg/dL to $\mu\text{mol/L}$: multiply by 88.4

From mg/L to $\mu\text{mol/L}$: multiply by 8.84

CONFIDENTIAL	FORM STATISTICAL ANALYSIS PLAN N° DGD-55-003 VERSION N° 2 DATED: 26 FEBRUARY 2018 (REF I011622)	F015830-01 Page 19 / 49
--------------	--	----------------------------

Listing of clinical laboratory evaluation will be presented in CSR appendix 16.2.8.

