#### ***Inclusion Criteria***

- Patient scheduled for a contrast enhanced MRI with DOTAREM® and who will be followed up for his/her renal impairment by one of the site study co-investigators.
- Patient must have moderate (eGFR 30-59 ml/min/1.73m^2) to severe (eGFR<30 ml/min/1.73m^2) and end stage (eGFR<15 ml/min/1.73m^2) renal impairment, dialysis patients can also be included.

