3. STATISTICAL METHODS

3.1. General considerations

At the end of the study, after the database lock, the statistical analysis will be performed by GUERBET Biostatistic team on the basis of the present document.

A quality control of the statistical analysis will be performed to ensure the reliability of the results.

Thorough description of all parameters reported will be presented. Summary tabulated results will be provided by assessment time if relevant or they will be replaced by the corresponding individual data listings if too few patients are concerned.

Tabulations of quantitative parameters will include the following summary statistics: Number of Patients / Mean / Standard Deviation / Minimum / Median / Maximum. If for a given parameter, the raw value has been collected with x decimal places, the mean, median and standard deviation will be rounded to x+1 decimal places, while the minimum and maximum values will be tabulated as reported with x decimal places.

Tabulations of frequencies for categorical data will include all possible categories and will display the number of observations in a category as well as the percentage (%). Percentages will be rounded to one decimal place. The category missing will be displayed only if there are actually missing values. Percentages will be calculated on the total of recorded (non missing) data.

The **baseline value** will be defined as the last available value prior to administration of the investigational product.

No statistical tests will be performed in this study. All statistics will be only descriptive.

SAS® Version: 9.4 will be used for all descriptive summaries.

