4. CHANGES IN THE CONDUCT OF THE STUDY OR PLANNED ANALYSES

The protocol was amended on one occurrence globally and twice in Turkey and twice in the United State of America (see protocol amendments for a full list of changes).

The global amendment has introduced following changes:

- The minimum number of patients with severe renal impairment was changed from 50% to 40% but this does not change the planned analysis as no analysis is foreseen considering the renal impairment status.
- The period of recruitment was extended. Initially 1000 patients were supposed to be included in the study with a minimum of 50% of patients with severe renal impairment. Despite the extension of the recruitment period, the sample size of 1000 patients was not reached by the end of the recruitment period. Thanks to better understanding of causality and risk factors conducting to NSF occurrence, safety and educational measures starting from 2012, the rate of NSF appears to be less than 1%, and the study was no longer powered to assess the NSF rate. For this reason and taken into account that the NSF was not a safety priority for the competent authorities anymore due to the low incidence, the recruitment was stopped in March 2015.
- Patients who had received DOTAREM® within 12 months prior to inclusion were included in the study.

The methodology of statistical testing is described in the protocol although no comparison is possible. No statistical tests will be presented in the report.

CONFIDENTIAL	FORM STATISTICAL ANALYSIS PLAN N° DGD-55-003 VERSION N° 2 DATED: 26 FEBRUARY 2018 (REF I011622)	F015830-01 Page 13 / 49
--------------	---	----------------------------

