	Male	xxx (xx.x%)
	Female	xxx (xx.x%)
	Missing (if applicable)	xx
Age (years) for Patients Older than Two Years Old	n	XXX
	Mean (SD)	xx.x (xx.x)
	Median	xx
	Min ; Max	xx ; xx
	Missing (if applicable)	xx
Age (month) for Patients Younger than Two Years Old	n	XXX
	Mean (SD)	xx.x (xx.x)
	Median	xx
	Min ; Max	xx ; xx
	Missing (if applicable)	xx
Weight (kg)	n	XXX
	Mean (SD)	xx.x (xx.x)
	Median	xx
	Min ; Max	xx ; xx
	Missing (if applicable)	xx
Height (cm)	n	XXX
	Mean (SD)	xx.x (xx.x)
	Median	xx

CONFIDENTIAL	FORM STATISTICAL ANALYSIS PLAN N° DGD-55-003 VERSION N° 2 DATED: 26 FEBRUARY 2018 (REF I011622)	F015830-01 Page 29 / 49
--------------	---	----------------------------

Total (N=XXX)		
Min ; Max	xx ; xx	
Missing (if applicable)	xx	
Body Mass Index (kg/m ²)	n	xxx
	Mean (SD)	xx.xx (xx.xx)
	Median	xx.x
	Min ; Max	xx.x ; xx.x
	Missing (if applicable)	xx
Body Mass Index by Class	n	xxx
	< 18.5 kg/m ²	xxx (xx.x%)
	≥ 18.5 and < 25 kg/m ²	xxx (xx.x%)
	≥ 25 and < 30 kg/m ²	xxx (xx.x%)
	≥ 30 kg/m ²	xxx (xx.x%)
	Missing (if applicable)	xx

SD: Standard Deviation.

%: (n row / n non missing) * 100.

Source: Listing 16.2.4.1.

Table 14.1.4.1.2 Demographic Characteristics – Safety Population

Same as table 14.1.4.1.2

Table 14.1.4.2 Magnetic Field - Safety Population

Total (N=XXX)		
Magnetic Field (Tesla)	n	xxx
	1.5	xxx (xx.x%)
	3	xxx (xx.x%)
	Missing (if applicable)	xx

%: (n row / n non missing) * 100.

Source: Listing 16.2.4.2.

Table 14.1.4.3 Current Renal Status - Safety Population

Total (N=XXX)		
Intensity of Impaired Renal Function	n	xxx
	Moderate	xxx (xx.x%)
	Severe	xxx (xx.x%)
	End Stage Renal Insufficiency or Dialysis	xxx (xx.x%)

CONFIDENTIAL	FORM STATISTICAL ANALYSIS PLAN N° DGD-55-003 VERSION N° 2 DATED: 26 FEBRUARY 2018 (REF I011622)	F015830-01 Page 30 / 49
--------------	--	----------------------------

		Total (N=XXX)
	Kidney Transplantation	xxx (xx.x%)
	Missing (if applicable)	xx
If End Stage Renal Insufficiency or Dialysis, Specify	n	xxx
	Hemodialysis	xxx (xx.x%)
	Peritoneal Dialysis	xxx (xx.x%)
	Missing (if applicable)	xx
Most Recent Serum Creatinine (μmol/L)	n	xxx
	Mean (SD)	xx.xx (xx.xx)
	Median	xx.x
	Min ; Max	xx.x ; xx.x
	Missing (if applicable)	xx
Estimated Creatinine Clearance (mL/min) for Patients Younger than 2 Years Old		xxx (xx.x%)
If Yes, Estimated	n	xx
	Mean (SD)	xx.xx (xx.xx)
	Median	xx.x
	Min ; Max	xx.x ; xx.x
	Missing (if applicable)	xx

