Listing 16.2.7.1 Adverse Events - All Included Population

Patient #	Population Flag	Primary System Organ Class Preferred Term Nature of the Event	Start Date	Seriousness/ Outcome	Intensity / Relationship to DOTAREM®	Administration of Concomitant Drug	Date of MRI Examination with DOTAREM®
xxxx		xxxxxxxxxxxxxxxxxxxxxx	mm/dd/yyyy	Yes:Death/ not yet recovered	Moderate/Not related	Yes :xxxxxx	mm/dd/yyyy
		xxxxxxxxxxxxxxxxxxxxxx	mm/dd/yyyy	No/recovered	Mild/unknown	No	

Etc.

AIP: All Included Population ; EP: Efficacy Population ; SP: Safety Population ; MRI: Magnetic Resonance Imaging.
MedDRA dictionary version 16.0.

Listing 16.2.8.1 Renal Status during Follow-up Period - All Included Population

Patient #	Population Flag	Date of MRI Examination with DOTAREM®	Follow-up Visit	Date of Last Renal Function Assessment	Serum Creatinine (umol/L)	Serum Creatinine (Entered)	Unit

AIP: All Included Population ; EP: Efficacy Population ; SP: Safety Population ; MRI: Magnetic Resonance Imaging.

Listing 16.2.9.1 Nephrogenic Systemic Fibrosis Suspicion/Diagnosis - All Included Population

Patient #	Population Flag	Date of MRI Examination with DOTAREM®	NSF Suspicion	Source of Suspicion	Confirmatory Biopsy	Specify if No	Date of the Biopsy	Final Diagnosis of NSF	Specify if No

CONFIDENTIAL	FORM STATISTICAL ANALYSIS PLAN N° DGD-55-003 VERSION N° 2 DATED: 26 FEBRUARY 2018 (REF I011622)	F015830-01 Page 47 / 49
--------------	---	----------------------------

AIP: All Included Population ; EP: Efficacy Population ; SP: Safety Population ; MRI: Magnetic Resonance Imaging ; NSF: Nephrogenic Systemic Fibrosis.

Listing 16.2.9.2 Medical Events during Follow-up Period except MRI examination - All Included Population

Patient #	Population Flag	Date of MRI Examination with DOTAREM®	Follow-up Visit	Date of FU Visit	Medical Event Category	Medical Event Date	Primary System Organ Class (Preferred Term) [Description]	Medical Event Specify

AIP: All Included Population ; EP: Efficacy Population ; SP: Safety Population ; MRI: Magnetic Resonance Imaging ; FU: Follow-Up.
MedDRA dictionary version 16.0.

Listing 16.2.9.3 MRI examination during Follow-up Period - All Included Population

Patient #	Population Flag	Follow-up Visit	Date of FU Visit	Product ATC Name	Product Class	Product Name	Volume Administered (mL)	Date

AIP: All Included Population ; EP: Efficacy Population ; SP: Safety Population ; ATC: Anatomical Therapeutic Chemical ; FU: Follow-Up.
WHO DD dictionary version 2015.

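### The follow-up creatinine table pools dialysis with non-dialysis patients, and its repeated-date rule does not screen out values dated on or before the MRI, so the mean change is hard to read as change in renal function

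*SAP*

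**What the plan says.** **Who is in the table.** The protocol's inclusion criteria state that "dialysis patients can also be included". At baseline the plan keeps renal categories apart: the shell of SAP Table 14.1.4.3 has rows for moderate, severe, "End Stage Renal Insufficiency or Dialysis" and "Kidney Transplantation", with a sub-field for hemodialysis or peritoneal dialysis.

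**What is tabulated at follow-up.** SAP 5.6.5: "Serum creatinine collected during the follow-up period will be tabulated as quantitative parameter by visit in raw data and change from baseline". The shell of Table 14.3.4.1 has three visit columns for the safety population, with n, mean, SD, median and range for the raw value and for the change. It has no row or column for renal status and no eGFR. SAP 3.11 marks subgroups as not applicable, and SAP 4 says that "no analysis is foreseen considering the renal impairment status".

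**Which values count.** Under SAP 3.1 the baseline value "will be defined as the last available value prior to administration of the investigational product". For follow-up, SAP 5.6.5 adds: "If during the follow-up visits, the date of last renal function assessment is replicated then only the first measurement will be taken into account". Listing 16.2.8.1 shows that the date recorded is the "Date of Last Renal Function Assessment", printed next to the date of the DOTAREM MRI.

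**The concern.** There are two separate weaknesses.

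**Pooling.** In a patient on dialysis, serum creatinine depends mainly on the dialysis and its timing rather than on remaining kidney function. This is general clinical knowledge, not a statement in the documents. Averaging such changes with those of patients not on dialysis gives a mean and an SD that describe neither group.

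**Dating.** The follow-up form takes the last assessment, whenever it was done. Protocol 3.3 attaches the 3-to-12-month window to the first follow-up visit, not to the blood sample, and allows the form to be completed from hospital notes. A rule for repeated dates implies that its authors expected old assessments to be reported again. But the rule looks only across follow-up visits, not back to the MRI or to the baseline sample.

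The stake is modest but real. Protocol section 1 mentions a possible gadolinium-related nephropathy in severe renal impairment. Serum creatinine is the only laboratory measure among the follow-up safety criteria in SAP 2.3, and Table 14.3.4.1 is its only planned summary.

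**Working it through.** The plan gives no SD, effect size or sample size for creatinine, so there is no figure to reproduce. The only numbers in SAP 5.6.5 are the unit factors, which agree with each other (88.4 / 10 = 8.84).

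**1. The date rule, followed as written.** Let a patient's baseline sample have date B, before the MRI date M. Suppose the first follow-up form reports that same sample as the last assessment, and the later forms report new samples.

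- Dates compared by the rule: B, and two later dates. None repeats, so nothing is removed.
- Change entered at follow-up 1: baseline value − baseline value = 0.
- If follow-up 2 also reported date B, the rule would drop the follow-up 2 value and keep the one at follow-up 1.

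No step in SAP 5.6.5 compares B with M.

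**2. Effect on the mean.** All inputs here are assumptions, since the documents supply none of them:

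- d = dialysis share
- g = share of the other patients whose follow-up value is the baseline value
- Δ = true mean change in patients not on dialysis, set at +30 µmol/L
- μ_D = mean change in dialysis patients, from −100 to +100 µmol/L

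Tabulated mean = (1 − d)(1 − g)Δ + d·μ_D

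| d | g | Arithmetic | Tabulated mean (µmol/L) |
|---|---|---|---|
| 0 | 10% | 0.9 × 30 | 27 |
| 0 | 20% | 0.8 × 30 | 24 |
| 0 | 30% | 0.7 × 30 | 21 |
| 10% | 0 | 27 ± 10 | 17 to 37 |
| 20% | 0 | 24 ± 20 | 4 to 44 |
| 30% | 0 | 21 ± 30 | −9 to 51 |
| 20% | 20% | 19.2 ± 20 | −0.8 to 39.2 |

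Pooling can lower, raise or reverse the mean. Repeated baseline values can only shrink the non-dialysis contribution towards zero.

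**3. Effect on the SD.** Assume an SD of change s_1 = 40 off dialysis and s_2 = 200 on dialysis, with Δ = 30 and μ_D = 0.

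Pooled variance = (1 − d)·s_1² + d·s_2² + d(1 − d)(Δ − μ_D)²

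- d = 10%: 1440 + 4000 + 81 = 5521, SD 74
- d = 20%: 1280 + 8000 + 144 = 9424, SD 97
- d = 30%: 1120 + 12000 + 189 = 13309, SD 115

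With 250 in place of 200 and equal means, the SD is √(0.9 × 1600 + 0.1 × 62500) = 88 at 10% and √(0.8 × 1600 + 0.2 × 62500) = 117 at 20%. The direction is the same; the size follows the assumed dialysis SD.

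**4. Scale.** Inverting the protocol's MDRD formula for a man aged 65 (k = 1), creatinine = (eGFR / (186 × 65^−0.203))^(−1/1.154) × 88.4 µmol/L. An eGFR of 59, 30 and 15 corresponds to about 115, 206 and 376 µmol/L. The eligible range is wide before any dialysis effect.

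**The case against.** Much of the case on the other side stands.

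- **A reader might infer that the SAP admits baseline values as follow-up.** It does not say so. It is silent on old dates, and its phrase about creatinine collected in the follow-up period, read with the baseline definition, may be meant to exclude them. The follow-up form (protocol Appendix 3) is not in the text, so whether it blocks earlier dates cannot be checked. What remains is that the phrase is not a programmable rule: an old value entered on a follow-up form can also be called collected then.
- **A reader might infer that the table cannot show any change in renal function.** That goes too far. It also gives the median and range, and the median is less sensitive to extreme dialysis values. Listing 16.2.8.1 shows the MRI date beside the assessment date, and Listing 16.2.4.3 gives renal status per patient, so re-analysis is possible. None is planned.
- **A reader might infer that a DOTAREM effect on the kidney is being hidden.** The documents do not support this. Nephropathy is background, not an objective. SAP 1.1 ties the general safety objective to inclusion and the MR examination. The study is single-arm with no tests, so even a corrected table could not attribute change to DOTAREM.
- **Transplant is not the same problem as dialysis.** Creatinine in a patient with a working graft still reflects renal function. A separate row is justified only because the baseline shell already treats transplantation as its own status.
- **Not splitting is a declared choice.** True, and no decision turns on a wider SD. But declaring the choice does not make the pooled mean easier to interpret.

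**Conclusion.** The point holds in a limited form. From the text alone it is established that follow-up creatinine is summarised over dialysis and non-dialysis patients together, with no split elsewhere, and that the repeated-date rule never looks at the MRI date. The pooled mean change and SD are therefore hard to interpret as change in renal function.

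The size cannot be fixed from the documents. They give no dialysis share, no SD of change and no frequency of old values; the 40% in protocol section 3 is a minimum for severe impairment, not a dialysis share. The figures above are illustrations. They show that a dialysis share of 10% to 30% could matter, and that repeated baseline values dilute the non-dialysis mean in proportion to their share.

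This is a cheap improvement to a secondary descriptive safety table, worth making before the report is written.

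**What to change.** 1. Present Table 14.3.4.1 separately for patients on dialysis at baseline (hemodialysis or peritoneal dialysis) and patients not on dialysis, with kidney transplant as its own row. Use the dialysis sub-field of Table 14.1.4.3, because the main category combines end-stage disease with dialysis, and state how a blank sub-field is treated.
2. In SAP 5.6.5, exclude follow-up creatinine dated on or before the DOTAREM MRI date. Apply this before the repeated-date rule, so that every excluded value is counted, and report the number excluded per visit.

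The cost is a few lines of SAP text and a split shell. The renal status, assessment date and MRI date are already in planned tables or listings, so no new data are needed. The downside is smaller groups.

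One limit remains. Dialysis started, or a kidney transplant received, during follow-up has no category of its own in Table 14.3.5.1, so a split by baseline status does not separate those patients. A footnote should say so.

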5.6.6. Vital signs, physical findings and other observations related to safety

Medical events will be coded in body systems and preferred terms using MedDRA dictionary v16.0.

Medical Event overview

Number and percentage of patient having undergone medical events will be tabulated by follow-up visit

MRI examination

Number of patients with MRI examination will be displayed by follow-up visit and by name of product. Name of product will be coded using WHO DD 2015 version and will be tabulated according to ATC code.

Medical Event by SOC and PT

Medical events will be displayed by follow-up visit and by SOC and PT.

Listing of medical events will be presented in CSR appendix 16.2.9.

CONFIDENTIAL	FORM STATISTICAL ANALYSIS PLAN N° DGD-55-003 VERSION N° 2 DATED: 26 FEBRUARY 2018 (REF I011622)	F015830-01 Page 20 / 49
--------------	---	----------------------------

6. LIST OF TABLES, FIGURES AND LISTINGS

6.1. Clinical study report in-text tables, figures and listings

6.2. Contents of clinical study report section 14

6.2.1. Demographic Data Summary and Figures

(Section 14.1 of ICH report)

6.2.1.1 *Disposition of Patients*

Table 14.1.1.1	Patient Overall Disposition - All Included Population
Table 14.1.1.2	Disposition by Visit - All Included Population
Table 14.1.1.3	Disposition by Site - All Included Population
Table 14.1.1.4	Centre Characteristics and Radiological Activities - All Centres
Table 14.1.1.5	Magnetic Fields of MR Equipments - All MR Equipments

6.2.1.2 *Protocol Deviations*

Table 14.1.2.1	Protocol Deviations - All Included Population
----------------	---

6.2.1.3 *Data Set Analysed*

Table 14.1.3.1	Analysis Data Populations - All Included Population
----------------	---

6.2.1.4 *Demographics and Baseline Characteristics*

Table 14.1.4.1.1	Demographic Characteristics - All Included Population
Table 14.1.4.1.2	Demographic Characteristics – Safety Population
Table 14.1.4.2	Magnetic Field – Safety Population
Table 14.1.4.3	Current Renal Status - Safety Population
Table 14.1.4.4	Pre-existing Risk Factor and Medical History - Safety Population
Table 14.1.4.5	Previous Examinations with GBCA - Safety Population
Table 14.1.4.6	Recent Surgery - Safety Population
Table 14.1.4.7	Concomitant Medications - Safety Population
Table 14.1.4.8	Indication of MRI Examination - Safety Population
Table 14.1.4.9	Premedications - Safety Population

CONFIDENTIAL	FORM STATISTICAL ANALYSIS PLAN N° DGD-55-003 VERSION N° 2 DATED: 26 FEBRUARY 2018 (REF I011622)	F015830-01 Page 21 / 49
--------------	---	----------------------------

6.2.2. Efficacy Data Summary Figures and Tables

(Section 14.2 of ICH report)

6.2.2.1 Primary Efficacy Variables

(Section 14.2.1 of ICH report)

Not applicable.

6.2.2.2 Secondary Efficacy Variables

Table 14.2.2.1 Overall Quality of Images - Efficacy Population

Table 14.2.2.2 Diagnostic Quality - Efficacy Population

6.2.3. Safety Data Summary Figures and Tables

(Section 14.3 of ICH report)

6.2.3.1 Extent of Exposure

Table 14.3.1.1 DOTAREM® Administration at Inclusion Visit - Safety Population

6.2.3.2 NSF suspicion and diagnoses

Table 14.3.2.1 Suspected NSF - Safety Population

Table 14.3.2.2 Confirmatory Biopsy and Final Diagnosis - Safety Population - Patient with Suspicion of NSF

6.2.3.3 Displays of Adverse Events

Table 14.3.3.1 Overall Safety Summary - Safety Population

Table 14.3.3.2 Treatment Emergent Adverse Events - Overall Summary - Safety Population

Table 14.3.3.3 Pre-injection Adverse Events by Primary System Organ Class and Preferred Term - Safety Population

Table 14.3.3.4 Treatment Emergent Adverse Events by Primary System Organ Class and Preferred Term - Safety Population

Table 14.3.3.5 Serious Treatment Emergent Adverse Events by Primary System Organ Class and Preferred Term - Safety Population

Table 14.3.3.6 Treatment Emergent Adverse Events with Relationship to DOTAREM® by Primary System Organ Class and Preferred Term - Safety Population

6.2.3.4 Listings of Deaths, Other Serious and Significant Adverse Events

Table 14.3.3.7 Listing of Deaths - Safety Population

Table 14.3.3.8 Listing of Serious Adverse Events - Safety Population

CONFIDENTIAL	FORM STATISTICAL ANALYSIS PLAN N° DGD-55-003 VERSION N° 2 DATED: 26 FEBRUARY 2018 (REF I011622)	F015830-01 Page 22 / 49
--------------	---	----------------------------

6.2.3.5 *Narratives of Deaths, Other Serious and Significant Adverse Events*

Not applicable.

6.2.3.6 *Display of Clinical Laboratory Data*

Table 14.3.4.1 Renal Status during Follow-up Period - Safety Population

6.2.3.7 *Vital Signs, Physical Findings and Other Observations Related to Safety*

Table 14.3.5.1 Medical Events except MRI Examination during Follow-up Period - Safety Population

Table 14.3.5.2 Contrast Media for MRI Examination during Follow-up Period - Safety Population

Table 14.3.5.3 Medical Events except MRI Examination during Follow-up Period by Primary System Organ Class and Preferred Term - Safety Population

6.3. Contents of clinical study report section 16.2

6.3.1. Disposition of Patients

(Section 16.2.1 of ICH report)

Listing 16.2.1.1 Visit Dates - All Included Population

Listing 16.2.1.2 Premature Withdrawal

Listing 16.2.1.3 Centre Characteristics and Radiological Activities

6.3.2. Protocol Deviations

(Section 16.2.2 of ICH report)

Listing 16.2.2.1 Protocol Deviations - All Included Population

6.3.3. Patients Excluded from Efficacy Analysis

(Section 16.2.3 of ICH report)

Listing 16.2.3.1 Analysis Data Populations - All Included Population

6.3.4. Demographic Data and Baseline Characteristics

(Section 16.2.4 of ICH report)

Listing 16.2.4.1 Demographics - All Included Population

Listing 16.2.4.2 Magnetic Field in Tesla - All Included Population

Listing 16.2.4.3 Current Renal Status - All Included Population

Listing 16.2.4.4 Risk Factors and Medical History - All Included Population

Listing 16.2.4.5 Previous Examinations with GBCA - All Included Population

CONFIDENTIAL	FORM STATISTICAL ANALYSIS PLAN N° DGD-55-003 VERSION N° 2 DATED: 26 FEBRUARY 2018 (REF I011622)	F015830-01 Page 23 / 49
--------------	---	----------------------------

Listing 16.2.4.6	Recent Surgery - All Included Population
Listing 16.2.4.7	Concomitant Medications - All Included Population
Listing 16.2.4.8	Indication of Current MRI Examination - All Included Population
Listing 16.2.4.9	Premedication - All Included Population

